In the R61 phase, we will examine the impact of SING on computational behavioral metrics of (Aim 1) Conditioned Hallucinations, (Aim 2) Social Reinforcement Learning, (Aim 3) Language Use, in 50 participants with voice hearing in the context of a psychotic illness. Following a screening visit to determine eligibility, these computerized tasks will be administered behaviorally, and an interview will elicit speech, prior to and following the full SING intervention (in 10 groups of 5 participants, each facilitated by a trained musical interventionist, during the first two years of the project). If SING meaningfully alters these computational task parameters (decision criteria outlined below), we will proceed to the R33 phase, wherein we will recruit a further 200 voice hearing participants with similar diagnoses. These participants will complete the same

tasks deemed mechanistically relevant in the R61 phase, prior to and following randomization to four different conditions (facilitated by an interventionist musician) that will deconstruct the possible active ingredients of SING along two dimensions: Activity and Ownership: (a) SING (n=50, Activity + and Ownership +), participants produce and perform their own song; (b) Karaoke (n=50, Activity + and Ownership -), participants perform karaoke, singing along to others music; (c) Pop Music (n=50, Activity – and Ownership -), participants will listen to popular music chosen by the music interventionists; and (d) Curated Playlists (n=50, Activity -, Ownership +), participants will curate playlists of popular music and listen to them together. This deconstruction will provide insights into the predictive processing framework, as applied to hallucinations and music, specifically, whether changes at higher, a-modal, hierarchical levels, particularly sense of self and active inference, influence precision weighted perceptual and social inferences more so than inactive experiences or experiences that do not engage sense of self.

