These experiments will require repeated performance of the Conditioned Hallucinations task and re-estimation of model parameters. Sensory conditioning effects tend to be stable across time³⁹⁻⁴¹, lasting from months to years. Fortunately, multi-sensory learning rarely generalizes to novel stimulus pairs and tasks⁴². Therefore, re-testing will make use of unique visual stimuli for each visit (matched for luminance, complexity, and contrast). Similarly, target auditory stimuli of different frequencies will be used. Preliminary data demonstrates the feasibility of this approach. **Figure 5** depicts data from one hallucinating participant, obtained 356 days following original data acquisition (blue) and five controls (white), obtained 28 days apart. Both the Conditioned Hallucinations effect and model parameters remain stable over time. Participants' thresholds for detection of a tone embedded in white noise will be determined using the maximum-likelihood-based QUEST¹⁸ method. During conditioning, all target auditory stimuli will be accompanied by a visual checkerboard stimulus (colors: red, green randomized across participants and sessions) present for the duration of the auditory stimulus presentation. Over a series of four training

blocks, participants will be presented first with stimuli presented at their individually-defined threshold for detection, and then increasingly with stimuli that are sub-threshold and absent. This will foster learning of the association between visual cue and tone specific to the particular session. **We predict** that SING will reduce the number of conditioned hallucinations in people who hear voices. We expect that computational analyses will reveal: 1) that people who hear voices have stronger perceptual priors, and 2) that the strength of these priors will be decreased following SING experience.

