R61 Aim 2 – Social Learning: Participants will play the social valuation task pre- and post-SING. As described above, this is a reinforcement learning task with distinct periods of high and low volatility. It is 120 trials long. For the first 40 trials, social volatility is low. For the remaining 80 trials, social volatility is high. The task also includes a non-social cue (green vs blue color) on each trial. Periods of volatility for the non-social cue are designed to be orthogonal to those for the social cue: this allows us to compare responses to both social and non-social cues. Participants will meet a gender-matched confederate for a brief interaction. Lab staff will review the task instructions with the subject and confederate together. The instructions include the information that the confederate's advice may be helpful or unhelpful because the confederate is responding to a separate reward scheme. The participant will complete a practice task to ensure that the instructions are clear. The participant will then watch the confederate complete a practice task. Having the participant watch the confederate practice helps to facilitate the fiction that the confederate is a real participant who needs to learn the task, and allows the participant to see the confederate make both helpful and unhelpful choices. We will use participant behavior to estimate prior expectations for volatility and prediction errors using the Hierarchical Gaussian Filter approach described above and previously employed with this task²⁶⁻²⁸. As above, parallel versions of the social valuation task with a different confederate and different card deck colors will be employed. **We predict** learning rates will be blunted under social volatility in people with AVH, and that this effect will normalize with SING

R61 Aim 3 - Qualitative Interviews: Participants will complete in-depth interviews both before and upon completion of SING. Interviews will focus on their previous experience with music, their experience of participating in the group intervention (post-intervention interview only), and their sense of self in three domains (narrative, embodied, intersubjective) related to the predictive processing theory of voices, psychosis and self.

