Previous experience with music. Participants will be asked to describe their current and past relationship with music to both situate the interview within their life experiences and to gain a richer sense of how participating affected their sense of self at post-intervention.

The experience of the group. Asking for participants' experience of participating in the group will (1) help us refine the intervention for the R33 phase to ensure that it is aligned with the proposed targets, and (2) provide us with rich descriptions of the group experience, providing a foundation for exploring changes in sense of self in the post-intervention interview regarding self-experiences that are often difficult to articulate.

Sense of self. The interviews will focus on how people construct representations of self, other, and world and how these representations coincide with their ability to construe, predict, and understand others. Interviews will focus on three aspects of sense of self: (1) *Narrative self*. The ways in which people define themselves will be explored in terms of both identity and social roles (e.g., parent, friend, patient, etc.). Interview questions will elicit perceptions of agency, specifically the ways in which participants construct representations of self and other. (2) *Embodied self*. Interview questions will elicit embodied experience,

particularly the sensations, perceptions, and feelings associated with constructions of self and other. (3) *Intersubjective self*. Participants will explore the experience of interacting with others. Participants will be asked to describe how they perceive others, the ways in which they feel similar and different to others, and the feelings associated with interacting with others in order to deepen our understanding of the ways they construe others.

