Qualitative Analysis: Grounded theory will be utilized to analyze interview data to develop an explanatory framework of how the intervention modifies participant's sense of self in relation to proposed targets⁴³⁻⁴⁵. Interview guides will be constructed in collaboration with stakeholders, including a co-investigator with lived experience of hearing voices ([name]), and piloted in a focus group of persons with 8-10 patients with SMI who hear voices who will not participate in the intervention. Interview guides and questions will be refined and targeted as themes emerge in the data collection phase. Due to: (1) scarcity of research on the topic, (2) uniquely personal yet often shared experiences of music hearing or making and of sense of self, shared sense of self, an extended inquiry is necessary and thus all R61 phase participants will be interviewed. A team of 4 qualitative researchers ([name], [name], [name], and [name]) will code interviews and develop a codebook^{46,47}. Each transcript will be analyzed in succession and codes will be developed using a consensual approach⁴⁸. The codebook will be refined as each transcript is coded, in line with the constant comparison method⁴⁴. Once a coding structure has been developed, the code structure will be applied and verified by a review of transcripts by the research team⁴⁹. The codebook developed for the pre-intervention interviews will be used to analyze the post-intervention interview to assess changes in self-experience.

Quantitative Analysis: We will analyze participant language use in transcribed quantitative interviews using LIWC⁵⁰. We will focus initially on I, Biological and Negative Emotional Words to focus on the signals identified in our previous work^{51,52} and to limit the number of statistical comparisons for which we need to correct with False Discovery Rate Correction⁵³. These three categories will comprise one step of our Go/No Go Decision (see below). However, we will also perform exploratory analysis on the other categories of speech in spirit of discovery and knowledge expansion. **We predict** that SING will ameliorate the excessive use of I, Biological and Emotional words in people with psychosis and hallucinations.

5. **Genetic Testing** N/A
6. **Subject Population:** *Provide a detailed description of the types of human participants who will be recruited into this study.*

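### Aim 3 word counts are not limited to prompts shared by both interviews, so a pre-post change in single-arm R61 may partly reflect different questions

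*Combined protocol and SAP*

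**What the plan says.** - **Interviews.** The research plan (Section I, item 4) says "an interview will elicit speech, prior to and following the full SING intervention". R61 Aim 3 describes an in-depth interview at each of these times. One of its topics is "their experience of participating in the group intervention (post-intervention interview only". The paragraph on the experience of the group describes that material as "providing a foundation for exploring changes in sense of self in the post-intervention interview".
- **Guide.** Under Qualitative Analysis: "Interview guides and questions will be refined and targeted as themes emerge in the data collection phase".
- **Scoring.** Under Quantitative Analysis: "We will analyze participant language use in transcribed quantitative interviews using" LIWC, the word-count software. Three categories (I, biological, negative emotion) are chosen, partly to "limit the number of statistical comparisons for which we need to correct with False Discovery Rate Correction". They also form one step of the Go/No-Go decision. No sentence restricts scoring to particular prompts or sections.
- **Test and decision rule.** Item 13 plans paired t-tests for Aims 1 to 3 and advances a metric to R33 if it changes by at least 2 SD from baseline. All 50 R61 participants receive SING.
- **The other two aims.** For Aim 1, "re-testing will make use of unique visual stimuli for each visit (matched for luminance, complexity, and contrast". For Aim 2, "parallel versions of the social valuation task with a different confederate and different card deck colors will be employed". No comparable rule is stated for the Aim 3 word counts.

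**The concern.** A word rate depends on what a person is asked to talk about as well as on the person. If the post-SING transcript contains a section on a shared musical activity and the pre-SING transcript does not, the two whole-transcript rates average over different topics. Question wording that changes during data collection can add to the mismatch.

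In a controlled comparison this might largely cancel. R61 has no control arm, so the added topic arrives at the same time as the intervention for everyone. A fall in I, biological or negative-emotion words could then come from the new section diluting the rest. A real fall could equally be hidden, or an apparent rise produced. At stake are the paired R61 result for language and, to a lesser degree, one input to the Go/No-Go decision.

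**Working it through.** **1. The plan's own figure.** Item 13 gives a difference of 0.01, an SD of 0.02, two-sided alpha 0.05, 80% power and at least 31 participants. The paired normal formula gives n = ((1.960 + 0.842) × 0.02/0.01)² = 31.4, which agrees with 31 to within rounding. That figure is for a conditioned-hallucination model parameter. No language effect is given, so n=31 serves below only as a low bound and n=50 as the case without drop-out.

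**2. How the topic enters.** Let f be the share of post-interview words that answer the group-experience prompts, and k the difference in word rate between that topic and the shared topics. With no SING effect and whole-transcript scoring, the expected pre-post shift is f × k. It is zero if k = 0. Neither f nor k is in the documents.

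**3. Effect on the paired t-test (assumed shifts).** Express the shift s in SDs of the pre-post change. The t statistic is then noncentral with n − 1 degrees of freedom and noncentrality s√n; for s = 0.2 and n = 50 this is 0.2 × 7.07 = 1.41. Two-sided rejection rates with no SING effect:

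| | s = 0 | s = 0.1 | s = 0.2 | s = 0.3 |
|---|---|---|---|---|
| n=50, alpha 0.05 | 5% | 10.7% | 28.4% | 54.8% |
| n=40, alpha 0.05 | 5% | 9.5% | 23.5% | 45.7% |
| n=31, alpha 0.05 | 5% | 8.4% | 19.0% | 36.6% |
| n=50, alpha 0.0167 | 1.7% | 4.5% | 15.4% | 36.9% |
| n=31, alpha 0.0167 | 1.7% | 3.3% | 9.2% | 21.1% |

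A simulation of 100,000 runs agreed with the alpha 0.05 rows at n=50 and n=31 to within 0.2 percentage points.

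The last two rows bound the effect of false discovery rate correction. Assuming Benjamini-Hochberg at 0.05 over three tests, any p ≤ 0.05/3 = 0.0167 is always rejected and no p above 0.05 ever is. The rate per category therefore lies between the alpha 0.0167 and alpha 0.05 rows.

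**4. Direction.** At s = 0.1, rejections on the side of the shift are 10.3% of studies out of 10.7% (n=50) and 7.8% out of 8.4% (n=31), so more than 90% in each case. The share is higher for larger shifts. Such rejections support the predicted decrease only if the added topic lowers these words; if it raises them, they contradict it.

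**5. What these shifts require.** Since s = f × k, a shift of 0.3 needs k = 0.3/f: 1.5, 1.0 or 0.6 SDs of change for f = 20%, 30% or 50%.

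**6. Effect on the 2 SD rule.** I read the rule as mean change against the baseline SD; item 13 does not say whether mean or individual change is meant. With equal SDs at both visits and pre-post correlation r (assumed), SD of change = baseline SD × √(2(1 − r)).

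| r | SD of change / baseline SD | 0.3 SD of change, in baseline SDs | Share of 2 SD bar |
|---|---|---|---|
| 0.3 | 1.183 | 0.355 | 17.7% |
| 0.5 | 1.000 | 0.300 | 15.0% |
| 0.8 | 0.632 | 0.190 | 9.5% |

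For topic alone to reach the bar, k must be 2/f baseline SDs: 10, 6.7 or 4 for f = 20%, 30% or 50%.

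**The case against.** The plan does not say that whole transcripts will be scored; it is silent. The interviews to be scored are called quantitative, which leaves room for a separate speech sample. The guides were still to be written and piloted, and prompts could be fixed then. The shifts in the table are round numbers with no anchor in the documents, so the rates show only that a paired t-test detects a non-zero mean. The Go rule is hardly touched, an advancing metric is studied again with randomisation in R33, and the study disclaims efficacy. Retest and time effects would confound a single-arm change even after the fix. In-depth interviews use varying probes, so few answers may follow identical wording.

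Much of this stands as a limit on size. The direction and amount of bias are unknown, and the decision impact is small. The silence does not remove the problem: the Aim 3 interview is the only pre-post interview described, so treating its transcripts as the ones scored is the likely reading, and nothing stops the post-only section being counted. If a separate standardised sample is meant, naming it settles the point. R33 protects only a metric that advances, and item 13 presents R61 and R33 together as a replication of SING's effect on language use, so the R61 result carries weight of its own. That other single-arm confounders remain is no reason to keep one that can be removed cheaply.

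**Conclusion.** The concern holds. The post-SING interview has a topic that the pre-SING interview lacks, question wording may evolve, and the plan sets no shared-prompt rule for the word counts. In a single-arm pre-post design, a change in word use can therefore mix a change of prompts with a change in the person.

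The size cannot be determined from the documents. Under the assumed shifts, false rejection at n=50 rises from 5% to between 11% and 55% uncorrected, with floors of 4.5% to 37% under false discovery rate correction. On the mean-change reading, the largest assumed shift is about 9.5% to 18% of the 2 SD bar, so topic alone is very unlikely to trigger a Go. The conclusion rests on the Aim 3 transcripts being the ones scored and on word rates differing by topic. The plan should be corrected on this point, mainly to protect the interpretation of the R61 paired language result.

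**What to change.** In Quantitative Analysis, name the transcripts that are scored and add a rule such as:

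> Confirmatory and Go/No-Go LIWC scores use only each participant's answers to prompts asked with the same wording at both of that participant's interviews. Answers in the group-experience section are excluded. Whole-transcript LIWC is exploratory.

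Keep a small core of shared prompts with fixed wording for this purpose; music and sense-of-self prompts can both contribute. The rest of the guide can evolve, and the qualitative use of the group topic is unaffected. Asking the core prompts before the group section is optional but would reduce carry-over.

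The cost is section tags in the transcripts, a few sentences in the plan and a fixed core in the guide, with no new visits or data. The downside is fewer scored words per participant. Retest and time effects remain, as may carry-over from the group discussion if the core prompts follow it. The core should be fixed in advance, because comparable text may not be recoverable once wording has drifted between a participant's two interviews.

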A total of 250 (50 in R61, 200 in R33) voice hearing patients (aged 18-65 years) meeting diagnostic criteria for DSM-V psychotic disorder, hearing voices at least once a day, and PANSS P3 (Hallucinations item) greater than 3.

7. **Subject classification:** *Check off all classifications of subjects that will be specifically recruited for enrollment in the research project. Will subjects who may require additional safeguards or other considerations be enrolled in the study? If so, identify the population of subjects requiring special safeguards and provide a justification for their involvement.*

- | | | |
|---|------------------------------------|--|
|  Children |  Healthy |  Fetal material, placenta, or dead fetus |
|  Non-English Speaking |  Prisoners |  Economically disadvantaged persons |
|  Decisionally Impaired |  Employees |  Pregnant women and/or fetuses |

- Yale Students Females of childbearing potential

NOTE: Is this research proposal designed to enroll children who are wards of the state as potential subjects?

Yes No

8. **Inclusion/Exclusion Criteria:** *What are the criteria used to determine subject inclusion or exclusion?*

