A total of 250 (50 in R61, 200 in R33) voice hearing patients (aged 18-65 years) meeting diagnostic criteria for DSM-V psychotic disorder, hearing voices at least once a day, and PANSS P3 (Hallucinations item) greater than 3, will be recruited from the local community via advertisement, from databases of ongoing Clinical Neuroscience Research Unit projects, community outpatient facility contacts and among the patients being recruited under [name] existing STEP clinic protocol, patients attending the Psychosis Clinic at the Connecticut Mental Health Center, Program for Recovery and Community Health, and the Connecticut Hearing Voices Network. Prior to study participation all patients will be evaluated for i) protocol eligibility; ii) interaction with the study team to determine participant's probability of completing the study; and iii) ability to cooperate with protocol procedures. The flow of all participants will be reviewed at weekly research meetings in consultation with the study team. Exclusion Criteria: i) DSM-IV substance abuse or dependence (past six months); ii) clinically significant medical conditions, head injury with neurological symptoms or unconsciousness; iii) mental retardation (IQ<70); iv) Non-English speaking; v) no less than 2 weeks of stable doses of psychotropic medications (to avoid transient effects of medication regiment change; medication type and dose will be carefully recorded and used as a covariate in all analyses); vi) Co-morbid mood or anxiety diagnosis; viii) clinically/behaviorally unstable and unable to cooperate with SING procedures. ix) Unstable medical condition based on medical history, physical examination and routine laboratory work-up, including a urine drug screen for illicit substance use (results will remain confidential, they will not be retained, and they will only be used for eligibility determination).

9. **Eligibility:** *How will eligibility be determined, and by whom?*

Eligibility will be determined initially by a telephone pre-screen and then confirmed with an in-person interview, by [name] and his team.

10. **Risks:** *Describe the reasonably foreseeable risks, including risks to subject privacy, discomforts, or inconveniences associated with subjects participating in the research.*

The risks from this study include 1) emotional distress, and 2) confidentiality.

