After phone screen, eligible participants will be invited to come to the CMHC for consent. A member of the research team will describe the study to potential participants, provide those who are interested with a consent form to read, answer all questions, and then obtain oral and written consent before beginning any study. Participants who wish to take the form home to consider it further before providing consent will have the option to do so. They may call study staff later to arrange a follow-up visit if they wish to consent to the study and continue the full clinical characterization. Otherwise, this may be completed at time of consent.

It is possible that some people with schizophrenia will have a conservator. They may wish to participate. In this case we will seek the person's assent and that of their conservator (by adding an optional conservator

signature on the document). We will also ensure that they understand the procedure and their relationships with the study team and their clinical team (that they are different). Since the conservator will need to sign the document too, this will ensure that there is an extended decision period for conserved persons. We will also arrange, with the person's assent, for [name] or one of the study team members to speak with the conservator before the person is randomized to the study.

7. **Evaluation of Subject(s) Capacity to Provide Informed Consent/Assent:** *Indicate how the personnel obtaining consent will assess the potential participant's ability and capacity to consent to the research being proposed. A member of study personnel will complete an in-person clinical assessment at intake. This assessment will include questions about the study procedures and possible risks to ensure the participant understands the study and is making an informed decision.*
8. **Non-English Speaking Subjects:** *Explain provisions in place to ensure comprehension for research involving non-English speaking participants. If enrollment of these participants is anticipated, translated copies of all consent materials must be submitted for approval prior to use.*

We will not recruit non-English speaking participants, they must be fluent in English to participate.

Note* If more than 2 study participants are enrolled using a short form translated into the same language, then the full consent form should be translated into that language for use the next time a subject speaking that language is to be enrolled.

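### Exclusion criterion v is worded the wrong way round: read literally, it excludes patients on stable medication, against its own stated purpose

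*Combined protocol and SAP*

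**What the plan says.** Section I, item 8 (Inclusion/Exclusion Criteria) runs inclusion and exclusion text together in one paragraph. The exclusion list opens with "Exclusion Criteria: i) DSM-IV substance abuse or dependence (past six months" and continues with numbered items. The fifth, item v, is "no less than 2 weeks of stable doses of psychotropic medications (to avoid transient effects of medication regiment change". The parenthesis that opens there gives the reason for the item and adds that "medication type and dose will be carefully recorded and used as a covariate in all analyses".

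The population is also described in Section I, item 6 (Subject Population), by age, diagnosis and "hearing voices at least once a day, and PANSS P3 (Hallucinations item) greater than 3". Nothing is said there about stability of medication. The recruitment and screening text in Section I, item 4 (Research Plan) is also silent on it.

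**The concern.** A rule in an exclusion list names what keeps a patient out. Item v names a state that, judged by its own reason, the investigators appear to want in their participants. Rule and reason therefore describe opposite groups, and item 8 is the only place where the rule is stated.

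Two things are at stake.

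- **Screening.** A screener who follows the wording and one who follows the reason would reach opposite decisions on the same patient.
- **Records.** If everyone follows the reason, each participant enrolled with two or more stable weeks still meets a listed exclusion as the protocol is written. The eligibility file then disagrees with the approved document.

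The item matters more in R61 than in R33. R61 has a single arm and compares each participant before and after SING, so a medication effect still settling between the two assessments would be counted in the change. Item v is the entry rule aimed at that problem. In R33, participants are randomized to four interventions.

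**Working it through.** No arithmetic applies; the check is one of logic and of cross-reading.

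**1. Direction of the list.** The other items in the list name conditions that bar entry: recent substance abuse or dependence, significant medical conditions, IQ below 70, a co-morbid mood or anxiety diagnosis, clinical instability. Item iv allows an outside check. It reads "iv) Non-English speaking", and Section III, item 8 (Non-English Speaking Subjects) says "We will not recruit non-English speaking participants, they must be fluent in English to participate". Meeting an item therefore means exclusion.

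**2. Item v read in the same direction.** No less than two weeks means a duration of two weeks or more. Let D be the time on stable doses at screening. As an exclusion, D ≥ 2 weeks leads to exclusion, and D < 2 weeks is not excluded by this item.

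**3. Rule against reason.**

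| Patient at screening | Item v read literally | Reason given in item v |
|---|---|---|
| Stable doses, D ≥ 2 weeks | excluded | gives no ground to exclude |
| Treatment changed, D < 2 weeks | not excluded | the group the reason is aimed at |
| No psychotropic medication, no recent change | not excluded | not addressed |

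The first two rows are reversed between the columns.

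**4. Is it repaired elsewhere?** Section I, items 4 and 6, are the other places where a stability rule would be expected, and neither has one. The sentence in item 8 is complete, so this is not lost or blacked-out text.

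**5. Does the covariate clause make up for it?** Only in part. Drug and dose do not record how recently either changed. The R61 analysis named in Section I, item 13 (Statistical Considerations) is a paired t-test, which has no covariate term, so the promise in item 8 is not carried into the named test. The clause does show that medicated patients are expected in the sample, which supports reading item v by its reason.

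**6. Size.** The planned enrolment is 50 in R61 and 200 in R33, 250 in all, under this one item. The documents do not say how many candidates have stable, recently changed or no medication, so the number affected under either reading cannot be estimated.

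**The case against.** The strongest reply is that the item explains itself. Its reason fits only one reading, and a clinician would see at once that an entry requirement has slipped into the wrong list. The setting also makes error less likely: a single site (Section III, item 1), one investigator and team deciding eligibility (Section I, item 9), weekly review of participant flow (Section I, item 8) and a psychiatric evaluation of every participant (Section I, item 11). Nothing in the documents indicates that the literal rule has been or would be applied, or that screeners in fact differ.

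Most of this stands, and it limits the consequence. A reader might infer from the literal wording that the trial will consist of recently changed or unmedicated patients, and that R61 is confounded by medication for that reason. The documents do not support that. Staff would have to act against the reason printed beside the rule. R61 also cannot separate SING from other changes over time however item v is worded, because it has no concurrent control; correcting the sentence would not remove that limitation.

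What the reply does not answer is the text itself. An operative criterion should not have to be read as the reverse of what it says, and following its evident intent puts the records at odds with the protocol.

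**Conclusion.** The point holds as an internal inconsistency in an eligibility rule: item v, as worded, excludes the group that its own reason gives no ground to exclude. It is very probably a drafting slip. The realistic consequence is misreading at screening and eligibility records that contradict the approved protocol. It changes no sample size, power figure, endpoint or Go/No Go rule, and its effect on enrolment cannot be quantified from the documents.

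The conclusion rests on two assumptions: that the items in the exclusion list are all meant in the same direction, which its neighbours and Section III, item 8 support, and that the parenthesis states the investigators' actual aim. It is worth correcting because the criterion decides who enters both phases and the correction is nearly free.

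**What to change.** Reconcile criterion v with its stated reason so that both describe the same excluded group. Either reword the item as an exclusion or move it to the inclusion text. No change to the two-week window is proposed, and the choice of rule rests with the investigators.

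The two routes may differ for one group. Moved unchanged into the inclusion text, the item could be read as requiring psychotropic medication, whereas an exclusion for recent change need not affect unmedicated patients. The new sentence should make plain which is meant.

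The cost is one sentence in a protocol amendment, with the same wording carried into any screening form that repeats the criterion.
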